6.1.3 Secondary Efficacy Endpoints

6.1.3.1 Key Secondary Efficacy Endpoints

• Event-free survival (EFS)

EFS is defined as the time from the date of randomization until the date of documented relapse (excluding relapse after PR), treatment failure or death from any cause within 30 days after the last dose of study drug, whichever occurs first [earliest of (relapse date, treatment failure date, death date) – randomization date + 1].

If a subject experiences relapse or death within 30 days after the last dose of study drug, the subject is defined as having EFS event related to either "relapse" or "death", and the event date is the date of relapse or death.

If a subject discontinues the treatment and fails to achieve any of the response of CR, CRp or CRi during the treatment period (subject with best response of PR or NR), the subject is defined as having EFS event related to treatment failure, and the event date is the randomization date. Subjects that discontinue the treatment with post-treatment disease assessment and best response of NE will be censored.

For a subject who is not known to have relapsed or treatment failure or death, EFS is censored at the date of last relapse-free disease assessment (last relapse-free disease assessment date – randomization date +1). Subject is not censored at HSCT. For subjects who are censored, last relapse-free disease assessment date refers to the subject's last disease assessment date. Subject without post-treatment disease assessment or without study treatment will be censored at randomization date.

EFS will be tested at the second interim and final analysis only when OS is rejected. No formal evaluation on EFS will be conducted at the first interim. During second interim analysis and final analysis, only death, relapse, treatment failure occurring on or prior to the cutoff date are counted as EFS events. Subjects without these events before cutoff date will be censored at the last relapse-free disease assessment date post-baseline on or before the cutoff date

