Disease assessment date refers to the date of central bone marrow aspiration or biopsy assessment. In the event that central bone marrow assessment is not performed or bone marrow is not adequate, local bone marrow assessment date will be used. If no aspirate or biopsy is available and subject is evaluated based on blast count from peripheral blood the date the peripheral blood sample is drawn will be used. If none of the above is available and subject is evaluated based on the presence of extramedullary leukemia, the assessment date of extramedullary leukemia will be used.

The following sensitivity analyses for EFS will be conducted:

- EFS will be defined similarly as the above primary analysis, however the date of the first new anti-leukemia therapy or the last treatment evaluation (when new anti-leukemia therapy date is not available), will be used as the event date of treatment failure.

- Sensitivity analysis of EFS will be performed to evaluate the impact of loss to follow-up on EFS. EFS will be defined similarly as the above primary analysis, however, subjects who discontinue the treatment due to "Lost to follow up" will also be considered as an EFS event (See Section 7.4.3.1 for details of "Lost to follow up" event), and the event date is withdrawal date or last evaluation date as collected on end of treatment, end of 30-day follow up, and end of long-term follow up CRF page whichever occurs first.
- EFS will be defined similarly as the above primary analysis with the following differences:
 - Subjects who discontinue the treatment and achieve best response of NR only will be defined as treatment failure and the event date is the randomization date
 - Subjects who discontinue the treatment and achieve best response of CR, CRp, CRi or PR and experience relapse will be defined as relapse and the event date is the date of first NR after CR, CRp, CRi or PR.
- EFS will be defined similarly as the above primary analysis, however, subjects who discontinue the treatment with post-treatment disease assessment and achieve best response of PR, NR or NE will be defined as treatment failure and the event date is the randomization date.
- Complete remission (CR) rate

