7.4 Analysis of Efficacy

There will be no efficacy analysis performed for the end of study report.

The significance levels at each interim and final analyses for each co-primary and secondary endpoints are specified in Table 4 below:

Table 4 Summary of Timing, Sample Size and Decision Guidance at the Planned Analyses

Analysis	Criteria for	Endpoint/	Efficacy B	Soundary*	Futility B	oundary*
	conduct of analysis (Projected timing)	Analysis Set	p-value (1-sided) at the Boundary	Approx. Observed HR at Boundary	p-value (1-sided) at the Boundary	Approx. Observed HR at Boundary
First Interim Analysis: CR/CRh rate	When 141 subjects are randomized into ASP2215 arm and at least 112 days (4 treatment cycles) post first dose or randomization (for subjects who received no study drug)	CR/CRh rate /2215 subjects in RAS	NA (0.0005 nominal)	NA	NA	NA
Second Interim	Approx. 129 OS	OS/ITT	0.00147	0.57	0.38674	0.95
Analysis:	events were observed	EFS/ITT	0.01519	0.67	0.30218	0.91
OS; EFS when null hypothesis of OS is rejected; CR rate when null hypotheses of both EFS and OS are rejected	Observed	CR rate/ITT	0.01519	NA	0.30218	NA
Final Analysis:	Approx. 258 OS	OS/ITT	0.02402	0.77	NA	NA
OS; EFS when	events were observed	EFS/ITT	0.01357	0.75	NA	NA
null hypothesis of OS is rejected; CR rate when null hypotheses of both EFS and OS are rejected	observed	CR rate/ITT	0.01357	NA	NA	NA

^{*:} P-value at both efficacy and futility boundaries (except the first interim) are based on 50% information fraction for OS, EFS and CR rate, and need update based on actual observed number of events at the second interim and final analysis.

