7.4.1 Analysis of Co-Primary Endpoint of OS (Second Interim and Final only)

The co-primary efficacy endpoint of OS will be analyzed on ITT for primary analysis. In order to compare the OS between ASP2215 and the salvage chemotherapy, the null hypothesis will be constructed:

• H_{01} : OS in ASP2215 is worse or equal to the OS in salvage chemotherapy

The accompanying alternative hypothesis is:

• H₁₁: OS in ASP2215 is better than the OS in salvage chemotherapy

The co-primary endpoint of the OS will be tested only at second interim and final analyses. The one-sided p-value for the above hypothesis test will be performed using the stratified log-rank test (primary test) with strata (per IRT) to control for response to first-line AML therapy and preselected salvage chemotherapy.

The SAS code to implement stratified log-rank will be similar to that shown below:

```
PROC LIFETEST;
    TIME time * status (1);
    STRATA stratification variables/group=treatment;
RUN;
```

The hazard ratio of the treatment effect along with 95% confidence interval will be calculated by the stratified Cox proportional hazard model. The same stratification factors will be applied to both the stratified log-rank test and the stratified Cox proportional hazard model. The same Cox proportional hazard model will be included as a sensitivity analysis for testing H_{01} .

The SAS code to calculate the hazard ratio of the treatment effect along with 95% confidence interval will be similar to that shown below:

```
PROC PHREG;

MODEL time * status (1) = treatment/RL;

STRATA stratification variables;
RUN;
```

Stratification variables will include response to first-line AML therapy and preselected salvage chemotherapy.

Kaplan-Meier survival plots will be used to describe the OS in each treatment group. Median OS and 95% confidence interval, survival rates at 6, 12, 24 and 36 months and 95% confidence interval will be estimated from the Kaplan-Meier curve using the SAS code similar to that shown below:

```
PROC LIFETEST DATA=XX TIMELIST=(XX XX XX);
    TIME time * status (1);
    STRATA treatment;
RUN;
```

Where TIMELIST option contains timepoint of interest to estimate survival rate.

Sensitivity analyses for OS include:

- The same analysis as primary analysis but on FAS
- The same analysis as primary analysis but on PPS

- Stratified Cox proportional hazard model with strata to control for response to first-line AML therapy and preselected salvage chemotherapy on ITT

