7.4.3 Analysis of Secondary Endpoints

7.4.3.1 Key Secondary Efficacy Analysis

The key secondary efficacy endpoint of EFS will be analyzed in the same manner as the co-primary endpoint of OS. In order to compare the EFS between ASP2215 and the salvage chemotherapy, the null hypothesis will be constructed:

• H₀₂: EFS in ASP2215 is worse or equal to EFS in salvage chemotherapy

The accompanying alternative hypothesis is:

• H₁₂: EFS in ASP2215 is better than EFS in salvage chemotherapy

To maintain the overall 1-sided Type I error rate at the 0.0245 significance level, the key secondary efficacy endpoint of EFS will be tested only at second interim and final analyses and only if the null hypothesis on OS (H_{01}) is rejected. The test significance levels of EFS endpoint at the second interim and final analyses are specified in Table 4.

The one-sided p-value for the above hypothesis test will be performed using the stratified log-rank test with strata (per IRT) to control for response to first-line AML therapy and preselected salvage chemotherapy.

The hazard ratio of the treatment effect along with 95% confidence interval will be calculated using stratified Cox proportional hazard model. The same stratification factors will be applied to both the stratified log-rank test and the stratified Cox proportional hazard model. The same Cox proportional hazard model will be included as a sensitivity analysis for testing H_{03} .

Kaplan-Meier survival plots will be used to describe the EFS in each treatment group. Median EFS and 95% confidence interval, EFS rates at 6, 12, 24 and 36 months and 95% confidence interval will be estimated from the Kaplan-Meier curve. The number and percentage of EFS event (relapse, death or treatment failure) and censoring will be summarized for each treatment group.

The sensitivity analyses for the key secondary efficacy endpoints of EFS include:

- The same analysis as primary analysis but on FAS
- The same analysis as primary analysis but on PPS
- Stratified Cox proportional hazard model with strata to control for response to firstline AML therapy and preselected salvage chemotherapy on ITT
- The same analysis as primary analysis but with the date of the first new anti-leukemia therapy after the end of study treatment or the last treatment evaluation date (when the date of new anti-leukemia is not available) will be used as the event date of treatment failure as defined in Section 6.1.3.1

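### EFS treatment failures all tie at day 1, yet no tie method is named for the EFS Cox model; under Breslow the HR and 95% CI move toward 1, slightly if fewer than half of controls fail on day 1

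*SAP*

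**What the plan says.** SAP Section 6.1.3.1 computes EFS as event date minus randomization date plus 1. For a subject who discontinues with PR or NR as the best response, "the subject is defined as having EFS event related to treatment failure, and the event date is the randomization date". Relapses, and deaths within 30 days of the last dose, keep their own dates. Subjects with a best response of NE are censored.

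Section 7.4.3.1 tests EFS by stratified log-rank and estimates the HR and 95% CI by stratified Cox. It states that the "endpoint of EFS will be analyzed in the same manner" as OS. It also uses the same Cox model as a sensitivity test of the EFS null hypothesis (numbered H03 in that sentence, although the EFS null is H02).

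The only Cox code is the OS template in Section 7.4.1, introduced by "The SAS code to calculate the hazard ratio of the treatment effect along with 95% confidence interval will be similar to that shown below". Its model line is "MODEL time * status (1) = treatment/RL". RL is the only option, and no tie method is named anywhere in the SAP.

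One EFS sensitivity analysis re-dates failures to new anti-leukemia therapy or last evaluation. The others keep day 1; one even enlarges the block, since subjects with "PR, NR or NE will be defined as treatment failure and the event date is the randomization date".

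**The concern.** A template without a tie option is adequate for OS, where ties are incidental. For EFS the endpoint definition itself creates a large tied block, and the HR then depends on an option that the plan leaves open.

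Under Breslow, the HR and CI printed beside a log-rank p-value can disagree with it. The Cox sensitivity test is affected in the same way. The re-dating analysis is meant to show what day-1 dating does to EFS. Because it also largely breaks the ties, its contrast with the primary HR would partly reflect tie handling.

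**Working it through.** **The plan's own figures reproduce.** Inputs from Section 4: 258 EFS events, HR 0.65 (3.9/6 = 0.65), 2:1 allocation, one-sided 0.0245.
- Power: sqrt(258 × 2/9) × |ln 0.65| = 7.572 × 0.431 = 3.26. Subtracting z = 1.97 gives 1.29, or 90.2%, matching the stated 90%.
- Table 4 final EFS boundary, one-sided p = 0.01357 (z = 2.209): exp(−2.209/7.572) = 0.747, matching 0.75.

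**Why the direction follows.** Take a single tied block with assumed counts (not from the SAP): 145/246 v 92/123 failing on day 1.
- Breslow solves to the ratio of proportions: 0.589/0.748 = 0.79. Its information is D·p(1−p) with D = 237 and p = 246 × 0.788/(246 × 0.788 + 123) = 0.612, so 56.3 and SE 0.133. The 95% CI is 0.61 to 1.02.
- Efron gives 0.68 (0.52 to 0.88).
- Log-rank: O − E = 145 − 237 × 2/3 = −13. The variance is 237 × 2/9 × (369 − 237)/368 = 18.9, so z = −2.99.

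The log-rank variance contains the factor (N − D)/(N − 1) = 132/368 = 0.36; the Breslow information does not. A clear log-rank result therefore sits beside a Breslow CI that includes 1.

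**Size in a whole trial.** The SAP gives no day-1 share, so it is varied. A 3.9-month control median requires a control share below 50%. Simulation: 246 v 123 subjects, exponential times, control median 3.9 months, HR 0.65, cut at 258 events, earliest events collapsed to day 1 or day-1 failure drawn separately with the same HR, unstratified and with 10 equal strata, 600 replicates per setting. The last column is a separate run (true HR 0.75, unstratified, 1500 replicates) that keeps trials close to p = 0.01357.

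| Control day-1 share (assumed) | Breslow HR | Efron HR | Log-rank p < 0.01357 but Breslow CI includes 1 | Breslow HR at the final boundary (upper limit) |
|---|---|---|---|---|
| 30% | 0.66-0.67 | 0.65 | 0% | 0.76 (0.98) |
| 40% | 0.68 | 0.65-0.66 | 0% | 0.77 (0.99) |
| 49% | 0.69 | 0.65-0.66 | 1-2% | 0.78-0.79 (1.01) |
| 60% | 0.72 | 0.65-0.66 | 7-10% | 0.80 (1.04) |
| 75% | 0.78-0.79 | 0.68-0.69 | 39-45% | 0.85 (1.09) |

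The fourth column is a percentage of the trials with log-rank p < 0.01357. Under Efron that figure is under 1%, and the boundary HR stays at 0.75-0.76 (upper limit 0.97-0.98). A two-sided 95% CI corresponds to one-sided 0.025, which is looser than 0.01357, so the disagreement is not caused by unequal levels.

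A second simulation held the control median at 3.9 months for shares below 50%. Breslow v Efron was 0.666 v 0.652 (30%), 0.673 v 0.649 (40%), 0.688 v 0.648 (49%) and 0.716 v 0.655 (60%).

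**Standard errors.** At 60% the Breslow model SE is 0.129 but its sampling SD is 0.099. For Efron these are 0.129 and 0.124. The CI width is the same under both methods, so the Breslow interval is shifted and too wide for its own estimator.

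**If the block has its own arm ratio** (block HR 0.55 to 0.75 instead of 0.65), the Breslow-Efron gap across the five shares is 0.01-0.02, 0.02-0.03, 0.03-0.04, 0.05-0.07 and 0.08-0.12. Disagreement is 0%, 0%, 0-6%, 2-29% and 9-80%. These runs add the day-1 share to later times with a 3.9-month median. The overall control median is then 3.9 × log2(2(1 − share)), about 1.9 months at 30% and 0.1 at 49%, so they illustrate a range, not the planned setting.

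**The case against.** - **No passage says Breslow is used.** The harm needs the default to apply and to be Breslow, and the code is only illustrative. This stands as a condition on the finding. It does not remove the gap, because no tie method is fixed.
- **Breslow may be a legitimate estimand.** Day 1 is an assigned point mass, and in the single-block example Breslow returns the day-1 risk ratio. That is fair for the point estimate. It does not rescue the interval, whose model SE exceeds the sampling SD and which can contradict the log-rank test.
- **Efron is imperfect.** With heavy ties it drifts too: 0.671 v 0.643 for the exact method at 70%, and 0.688 v 0.635 at 80%. This stands. Efron is still much closer than Breslow (0.759 and 0.804).
- **The effect is small on the SAP's own medians, and no decision turns on it.** Both are true. Table 4's HR column is labelled "Approx. Observed HR at Boundary" and its boundary p-values "need update based on actual observed number of events at the second interim and final analysis".
- **The effect on the re-dating contrast is not quantified.** Correct. That analysis also changes the event dates, so the part due to ties cannot be stated in advance.
- **Version 4.0 plans no further efficacy analysis** (Section 6.1). Correct; this limits where the change applies.

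**Conclusion.** The point holds and is minor. The plan builds a tied block into EFS and leaves open the option that governs the HR, its CI and the Cox sensitivity test. With a control day-1 share below 50%, Breslow raises an HR of 0.65 by about 0.01 to 0.04 and almost never contradicts the log-rank test. The effect is material only if most controls fail on day 1. That would put the control median at day 1, against the planned 3.9 months, although the planned 10% control CR rate does not exclude it if CRp and CRi add little.

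The conclusion rests on three assumptions: Breslow as the applied default, the assumed day-1 shares, and an effect close to proportional at HR 0.65. Under them the shift is conservative and cannot create a false EFS claim. If both medians are forced to 6 and 3.9 months with large day-1 shares, the later hazard can favour control and the shift need not be toward 1. At shares of 45% v 30%, for example, Breslow gives 1.13 and Efron 1.08.

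**What to change.** In Section 7.4.3.1, state TIES=EFRON on the PHREG MODEL statement for the EFS Cox model. Apply it to every EFS sensitivity analysis that keeps day-1 dating, that is, all except the one re-dating failures to new therapy or last evaluation. TIES=EXACT would also be defensible and is closer to the simulated HR when the block is very large.

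The section already plans that "The number and percentage of EFS event (relapse, death or treatment failure) and censoring will be summarized for each treatment group". Show the treatment-failure counts by arm beside the HR, so that the reader sees the size of the block.

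The cost is one code option and the placement of a count already planned. The test, boundaries and sample size do not change. As no efficacy analysis is planned for the end-of-study report, the change applies to the retained EFS text and to any rerun.

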- e. For subjects who plan to proceed to HSCT and resume ASP2215 treatment after HSCT, AE collection will continue until the start of the HSCT conditioning regimen and AE collection will resume upon the resumption of ASP2215 treatment until 30 days after the last dose of study drug. For subjects who do not plan to resume ASP2215 treatment after HSCT, AE collection will continue until the start of the HSCT conditioning regimen or 30 days after the last dose of study drug, whichever comes first. However, the following AE/SAEs will continue to be collected until 30 days after the last dose of study drug, regardless of the time of the HSCT conditioning regimen:
 - Any study drug related AE that is ongoing will be followed until resolved
 - Any SAE that is deemed to be related to study drug by the investigator
 - Any event of veno-occlusive disease (VOD) of the liver, cardiac failure, Grade 3 or higher QT prolongation, rhabdomyolysis, drug-induced liver injury, or PRES
 - Adverse events leading to death
- f. Telephone contact with the subject is sufficient unless any assessment must be repeated for resolution of treatment-related AEs.
- g. Only SAE data that is related to ASP2215 will be collected.
- h. Telephone contact every 3 months. Ad hoc contact will be required during interim analysis.
- i. Includes Brief Fatigue Inventory, Functional Assessment of Chronic Illness Therapy—Dyspnea-Short Forms, Functional Assessment of Cancer Therapy—Leukemia and dizziness and mouth sores items. The BFI will be administered at pre-HSCT/end of treatment visit. Functional Assessment of Cancer Therapy—Dyspnea-Short Forms, Functional Assessment of Cancer Therapy—Leukemia and dizziness and mouth sores items will be administered at pre-HSCT/end of treatment visit.
- j. Ophthalmologic assessment to be performed by visual acuity measurement and ophthalmoscopy, at the Pre-HSCT/end of treatment (+/- 7 days). In symptomatic subjects, the ophthalmologic assessment should also include slit lamp biomicroscopy, visual fields and optical coherence tomography (OCT).
- k. If possible, patient reported outcome measures should be performed prior to any other assessments on that visit day.

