Subjects who have a donor identified and achieve a response allowing them to undergo HSCT per each institution's assessment can undergo HSCT without leaving the study. However, ASP2215 should be stopped and a pre-HSCT visit should be performed prior to starting the conditioning regimen for HSCT. ASP2215 can be resumed after stem cell transplantation if the following conditions are met:

- Subject is between 30 60 days post HSCT
- Subject has had successful engraftment as demonstrated by absolute neutrophil count $(ANC) \ge 500/mm3$ and platelets $\ge 20000/mm3$ without transfusions
- Subject does not have \geq grade 2 acute graft-versus-host-disease (GVHD)
- Subject is in CRc

For subjects resuming treatment, subjects will follow the procedures listed under subsequent cycles day 1 in the Schedule of Assessments. Subjects who do not resume ASP2215 will be followed for OS endpoint.

After treatment discontinuation, subjects will have a pre-HSCT/end of treatment visit within 7 days after treatment discontinuation, followed by a 30-day follow-up visit in which a telephone contact with the subject is sufficient unless any assessment must be repeated for resolution of treatment-related AEs. After which the subjects will enter the long-term follow-up period for collection of patient reported outcome (PRO) using EQ-5D-5L, subsequent AML treatment, remission status and survival (cause of death and date of death). The long-term follow-up will be every 3 months, for up to 3 years from the subject's end of treatment visit.

Two interim analyses by an Independent Data Monitoring Committee (IDMC) will be conducted. The first interim analysis is planned when approximately 141 subjects are randomized into ASP2215 arm and at least 112 days (4 treatment cycles) post first dose or randomization (for subjects who received no study drug). The first interim analysis will be performed to evaluate the efficacy endpoint of CR/CRh rate and the study conduct will not be impacted by the result of the CR/CRh rate.

The second interim analysis will be performed when approximately 50% of the planned total number of deaths (death events =129 of planned 258 death events) by any cause have occurred. The second interim analysis will be utilized to determine whether the study should be terminated earlier than planned if ASP2215 has more favorable or harmful outcome than

the salvage chemotherapy group. Details of the interim analyses are described in Section 7.10.

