CR rate is defined as the number of subjects who achieve the best response of CR divided by the number of subjects in the analysis population. As a sensitivity analysis, CR rate prior to HSCT will be defined as the number of subjects who achieve CR prior to HSCT divided by the number of subjects in the analysis population.

CR rate will be tested at the second interim and final analysis only when both OS and EFS are rejected. No formal evaluation on CR rate will be conducted at the first interim.

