6.1.3.3 Response Definition

Response to treatment will be defined per modified Cheson criteria [2003] as outlined below.

Response will be derived using myeloblast counts from centrally evaluated bone marrow aspirate if it's adequate. In case of non-adequacy, myeloblast counts from centrally evaluated bone marrow biopsy will be used. If neither central bone marrow aspirate nor biopsy is available, myeloblast counts will be imputed with locally evaluated bone marrow aspirate, if not available, locally evaluated bone marrow biopsy assessments. Centrally evaluated hematology results including ANC, platelet count and blast count in peripheral blood will be used in response derivation. Missing central hematology results will be imputed with local hematology results as collected on the eCRF.

Response will be derived for all post-baseline visits on or after 21 days from first dosing date.

• Complete Remission (CR)

For subjects to be classified as being in CR at a post-baseline visit, they must have bone marrow regenerating normal hematopoietic cells and achieve a morphologic leukemia-free state and must have an absolute neutrophil count (ANC) $\geq 1 \times 10^9$ /L and platelet count $\geq 100 \times 10^9$ /L, and normal marrow differential with < 5% blasts, and they will be red blood cell (RBC) and platelet transfusion independent (defined as 1 weeks without RBC transfusion and 1 week without platelet transfusion). There must be no presence of Auer rods. There should be no evidence of extramedullary leukemia. The blast counts in peripheral blood must be $\leq 2\%$.

• Complete Remission with Incomplete Platelet Recovery (CRp)

For subjects to be classified as being in CRp at a post-baseline visit, they must achieve CR except for incomplete platelet recovery ($< 100 \times 10^9/L$).

• Complete Remission with Incomplete Hematological Recovery (CRi)

For subjects to be classified as being in CRi at a post-baseline visit, they must fulfill all the criteria for CR except for incomplete hematological recovery with residual neutropenia $< 1 \times 10^9 / L$ with or without complete platelet recovery. RBC and platelet transfusion independence is not required.

• Composite Complete Remission (CRc)

For subjects to be classified as being in CRc at a post-baseline visit, they must either achieve CR, CRp or CRi at the visit.

• Complete Remission with Partial Hematologic Recovery (CRh)

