At a post baseline visit, subjects will be classified as CRh if they have marrow blasts < 5%, partial hematologic recovery ANC >= 0.5×109 /L and platelets >= 50×109 /L, no evidence of extramedullary leukemia and cannot be classified as CR. The blast counts in peripheral blood must be $\leq 2\%$

• Partial Remission (PR)

For subjects to be classified as being in PR at a post-baseline visit, they must have bone marrow regenerating normal hematopoietic cells with evidence of peripheral recovery with no (or only a few regenerating) circulating blasts and with a decrease of at least 50% in the percentage of blasts in the bone marrow aspirate with the total marrow blasts between 5% and 25%. A value of less or equal than 5% blasts is also considered a PR if Auer rods are present. There should be no evidence of extramedullary leukemia.

• Not Evaluable (NE)/No Response (NR)

In the situation where no bone marrow assessments are performed or myeloblast value is missing, blast value from peripheral blood is missing or <=2%, and extramedullary leukemia is missing or not present, the response will be classified as not evaluable (NE). In any case response cannot be categorized as CR, CRp, CRi, PR or NE, it will be categorized as NR

Relapse

Relapse after CR, CRh, CRp or CRi is defined as a reappearance of leukemic blasts in the peripheral blood (> 2%) or $\ge 5\%$ blasts in the bone marrow aspirate not attributable to any other cause or reappearance or new appearance of extramedullary leukemia.

Relapse after PR is similarly defined with reappearance of significant numbers of peripheral blasts and an increase in the percentage of blasts in the bone marrow aspirate to > 25% not attributable to any other cause or reappearance or new appearance of extramedullary leukemia.

Best Response

Best response is defined as the best measured response to treatment for all visits (in the order of CR, CRp, CRi, PR, NR and NE) post-baseline. Subjects who achieve the best responses of CR, CRp, CRi, or PR will be classified as responders. Subjects who do not achieve at least a best response of PR will be classified as non-responders.

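### Does testing CR rate without a cut at HSCT tilt the H03 comparison towards ASP2215 enough to change which version is tested?

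*SAP*

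**What the plan says.** **Endpoint.** Section 6.1.3.1: "CR rate is defined as the number of subjects who achieve the best response of CR", divided by the analysis population. Section 6.1.3.3 sets the window: "Response will be derived for all post-baseline visits on or after 21 days from first dosing date", with no upper limit, and "Best response is defined as the best measured response to treatment for all visits". None of these stops at HSCT. The inputs are measured values: "Response will be derived using myeloblast counts from centrally evaluated bone marrow aspirate", with central biopsy and then local marrow as fallbacks, plus blood counts.

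**Test.** Section 7.4.3.1 tests H03 on ITT with a stratified CMH test, only after OS and EFS have been rejected. Table 4 sets one-sided 0.01357 at the final analysis.

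**Visits after HSCT.** Section 3.2.1 lets ASP2215 be resumed under conditions that include being in CRc. For those who resume, "subjects will follow the procedures listed under subsequent cycles day 1 in the Schedule of Assessments", which includes laboratory tests and marrow sampling. By contrast, "Subjects who do not resume ASP2215 will be followed for OS endpoint". In section 2, Table 3, marrow and laboratory tests appear only at the pre-HSCT/end of treatment visit. Long-term follow-up is "Telephone contact every 3 months"; section 3.2.1 says it collects "subsequent AML treatment, remission status and survival" data.

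**Pre-HSCT version.** Sections 6.1.3.1 and 7.4.3.1 define the CR rate prior to HSCT as a sensitivity analysis with the primary method. Section 7.4.6 does the same for CR/CRh.

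**The concern.** Resumption after HSCT requires CRc, not CR. An ASP2215 subject transplanted in CRp or CRi can therefore engraft, resume treatment, recover counts and be classified as CR at a scheduled visit. A chemotherapy subject in the same state has no post-HSCT visit in the SAP at which this would be recorded. Telephone contact does not help, because response is derived from marrow and blood values. Death, by contrast, can be learned by telephone in either arm, so the fact that OS is not cut at HSCT does not answer the point.

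H03 sits inside the type I error hierarchy. If part of a CR difference came from who was still scheduled for a marrow after transplant, the confirmatory claim would partly reflect the visit schedule. The between-arm CR/CRh summary in section 7.4.6 has the same feature.

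**Working it through.** **Is the tested version really uncut?** Yes. The definition and the window carry no stop at HSCT, and a separate pre-HSCT rate would be redundant if the main one already stopped there.

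**Is scheduled ascertainment one-sided?** As written, yes:

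| Group after HSCT | Marrow and laboratory visits described |
|---|---|
| ASP2215, resumes | Subsequent-cycle day 1 schedule (3.2.1; Table 1) |
| ASP2215, does not resume | None in Table 3 after the pre-HSCT visit |
| Chemotherapy | None in Table 3 after the pre-HSCT/end of treatment visit |

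Two things narrow this. Footnote k of Tables 1 and 2 allows clinically indicated marrows in both arms, and section 6.1.3.3 accepts local results. Also, subjects in CRc have marrows only 1 month after remission and then every 3 cycles (Table 1, footnote k).

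**Reproducing the plan's power.** Inputs: 246 v 123, CR 25% v 10%, one-sided 0.0245 (section 4). Normal approximation, pooled null variance:

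power = Φ[(p_T − p_C − z·SE0) / SE1]

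- Pooled p = (246 × 0.25 + 123 × 0.10)/369 = 0.20
- SE0 = √[0.20 × 0.80 × (1/246 + 1/123)] = 0.04417
- SE1 = √[0.25 × 0.75/246 + 0.10 × 0.90/123] = 0.03865
- z = 1.9686: (0.15 − 1.9686 × 0.04417)/0.03865 = 1.63, power 94.9%

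This agrees with the stated figure of more than 90%. At 0.01357 (z = 2.2095) the power is 91.2%.

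**Size of a possible lean (illustration only).** Assume a 10% pre-HSCT CR rate in both arms, k CRs first recorded after HSCT in ASP2215 and m in chemotherapy. Each adds 1/246 = 0.41 points or 1/123 = 0.81 points. Same formula at one-sided 0.01357, for example k = 5, m = 0:

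- p_T = 0.10 + 5/246 = 0.1203; pooled p = 0.1136
- SE0 = 0.03504; SE1 = 0.03409
- (0.0203 − 2.2095 × 0.03504)/0.03409 = −1.67, giving 4.7%

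| k (ASP2215) | m (chemotherapy) | Normal approximation | Exact enumeration of the same z test |
|---|---|---|---|
| 0 | 0 | 1.4% | 1.15% |
| 2 | 0 | 2.3% | 2.03% |
| 5 | 0 | 4.7% | 4.28% |
| 5 | 1 | 2.9% | 2.55% |
| 5 | 2 | 1.8% | 1.48% |

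At m = 2.5 the proportions are equal and the normal figure returns to 1.4%. All figures ignore the strata and come before the gating on OS and EFS. The values of k and m are assumptions; the SAP gives nothing from which to derive them.

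**Price of testing the pre-HSCT version.** If the planned 25% includes post-HSCT CRs, power against 10% at 0.01357 falls from 91.2% to 87.2% (at 24%) or 82.0% (at 23%).

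**The case for a change.** The strongest case for a change is that swapping the two versions costs only wording. Both are already planned, and a handful of one-sided late CRs could roughly triple the nominal rejection rate (1.4% to 4.7%). A sensitivity analysis exposes the effect, but the alpha-controlled claim still rests on the version open to it.

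The description of the schedule stands. Three points keep it from being a defect.

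- **The uncut version is coherent.** It matches OS and EFS, neither of which is cut at HSCT in the main analysis. HSCT takes place within the study, and resumed ASP2215 is part of that arm's planned treatment, so a CR on resumed drug is a response to the assigned strategy.
- **The cut has asymmetries of its own.** It ends the chance of CR earlier in whichever arm transplants more or sooner, and transplantation rate is itself compared between arms. It also leaves the pre-HSCT difference in place, since MEC and FLAG-IDA subjects have fewer scheduled marrows (Table 2, footnote k).
- **The table above measures type I error only if pre-HSCT CR is taken as the right target.** If the extra CRs are real and chemotherapy has none, H03 is false as the SAP defines CR.

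The absence of post-HSCT visits in the chemotherapy arm is also partly read from silence. Table 2, footnote k, repeats marrows after CRc without stating a stop at HSCT, and the protocol is not at hand.

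**Conclusion.** No change to the plan. The tested CR rate counts CRs first recorded after HSCT, and the scheduled visits that could record them are described only for subjects who resume ASP2215. Scheduled ascertainment, though not necessarily actual ascertainment, may therefore lean towards ASP2215. The amount cannot be derived from the SAP. The 2.3% and 4.7% figures rest on assumed counts of 2 and 5 late CRs, none in chemotherapy, and a common 10% pre-HSCT rate.

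Which version carries H03 is an estimand choice and a fair trade-off, and the alternative is already pre-specified with the same method. Sections 1 and 6.1 state that efficacy was reported on the 17 SEP 2018 cutoff and will not be analysed again, so changing the tested variable now would be post hoc. For interpretation, the H03 result is best read beside the planned pre-HSCT rate. The number of CRs first recorded after HSCT in each arm is the difference between the two planned numerators.
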